		Day -1	Day 1	Washout			Day 1	Day 2	Days 3-4		Day 5 ¹
				Day 2	Days 3-5	Days 6-7					
Pregnancy test	X								X	Serum testing at Day -1	
Columbia-Suicide Severity Rating Scale	X									X	
Genetic sample (optional)	X										
Study intervention: GSK3640254 200 mg (capsule or tablet)		X				X					Participants will fast overnight for at least 10 hours prior to dosing; be provided a moderate fat meal, a high fat meal, or no meal 30 minutes prior to dosing; and be provided standardized meals ≥4 hours postdose. See Section 4.1.
Serial PK sampling		X	X	X		X	X	X	X		Blood collection for PK analysis of GSK3640254 will be collected within 40 minutes prior to dosing and 1, 1.5, 2, 2.5, 3, 3.5, 4, 4.5, 5, 6, 8, 12, 24, 48, 72, and 96 hours postdose in each period.
AE review		←-----X-----→									
SAE review		←-----X-----→									
Concomitant medications		←-----X-----→									

AE = adverse event; D = day; ECG = electrocardiogram; PK = pharmacokinetic; SAE = serious adverse event.

1 Evaluations scheduled for Day 5 in Period 4 will also be performed for participants who discontinue early.

- The timing and number of planned study assessments, including safety, PK, or other assessments may be altered during the course of the study based on newly available data (e.g., to obtain data closer to the time of peak plasma concentrations) to ensure appropriate monitoring.
- Any changes in the timing or addition of time points for any planned study assessments as the result of emerging PK data from this study must be documented and approved by the relevant study team member and then archived in the sponsor and site study files but will not constitute a protocol amendment. The Institutional Review Board/Independent Ethics Committee will be informed of any safety issues that constitute a substantial amendment and require alteration of the safety monitoring scheme or amendment of the informed consent form. The changes will be approved by the competent authorities and the ethics committee before implementation.

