2.3. Benefit/Risk Assessment

Based upon preclinical and clinical studies, the major risks for GSK3640254 are GI intolerability (e.g., abdominal pain and diarrhea) and toxicity (e.g., single-cell parietal cell necrosis), prolongation of the QTc, and neuropsychiatric safety. Reproduction of preclinical GI toxicity findings would be unlikely during the limited dosing of GSK3640254 in this study. One preclinical study showed 1 dog with an increased QTc interval when given a single dose of GSK3640254. As described in Section 2.2.2, a cardiodynamic analysis of healthy participants in Study 207187 was conducted. A final model from the MAD data showed a QT effect ($\Delta\Delta\text{QTcF}$) of GSK3640254 could be predicted to be 5.38 ms (90% CI: 1.66 to 9.10) and 6.70 ms (90% CI: 2.79 to 10.61) for the 200 mg (1779 ng/mL) and 320 mg (2154 ng/mL) doses, respectively, on Day 14. Based on this concentration-QTc analysis, a QTcF effect above 10 ms could be excluded up to GSK3640254 plasma concentrations of approximately 2000 ng/mL (corresponding to doses approximately \leq 200 mg QD; note, 200 mg QD is the dose used in this study). Importantly, there were no abnormal clinically significant arrhythmias or QTc prolongations (values $>$ 500 ms or increases $>$ 60 ms from Baseline) in Study 207187. This study contains specific cardiac exclusion criteria, has ECG monitoring (at T_{max} once GSK3640254 attains steady state concentration), and has QTcF-based stopping criteria.

Finally, the protocol will exclude potential participants with any significant pre-existing psychiatric condition or positive (abnormal) response confirmed by the investigator on a clinician (or qualified designee)-administered Columbia Suicide Severity Rating Scale (C-SSRS). The C-SSRS assessment will also be administered by a clinician (or qualified designee) during the on-treatment portion of the study.

To ensure the overall safety of participants (including, but not limited to, the risk of GI intolerability, QTc prolongation, and neuropsychiatric safety), this clinical study will include healthy adults who will receive clinical, ECG, and laboratory evaluations during their participation. More detailed information about the known and expected benefits and risks and reasonably expected AEs of GSK3640254 may be found in the CIB [GSK Document Number [2018N379610_00](#)].

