	
predominant AEs, with a trend for increasing neurologic and psychiatric AEs with increasing dose (based on TQT and Phase 2b studies). No exposure-response relationship was seen for select neurologic and psychiatric AEs (based on TQT and Phase 2b studies). Central nervous system penetration data for GSK3532795 and GSK3640254 in rats demonstrate a similarly low brain distribution/penetration.
 
In the multiple ascending dose part of first time in human study 207187, clinically relevant preferred terms from the system organ class nervous system were experienced by 5 subjects (somnolence, disturbance in attention, and lethargy) and showed that the greatest incidence arose in the GSK3640254 200 mg arms (Cohorts 5 and 7), but no dose/AE relationship was apparent. Seven subjects experienced five psychiatric AEs: agitation, abnormal dreams, insomnia, depressed mood, and nightmare. All events were mild in intensity and considered by the investigator to be unrelated to study drug, apart from one subject from the blinded 320 mg arm who experienced lethargy which was considered related to study drug
	
AEs during their participation in the study; there are individual clinical stopping criteria and monitoring based upon incidence and intensity of treatment-emergent psychiatric AEs (Section 7.1.4 and Section 8.2.5).
 
Participants will be housed throughout study conduct to ensure rapid diagnosis and management of any potential event.
 
The C-SSRS will be administered during and after the treatment phase of the study. In the event of a positive (abnormal) response confirmed by the investigator, the participant will discontinue from the trial and the investigator will arrange for urgent specialist psychiatric evaluation and management. Guidance for the investigator on the management of emergent psychiatric symptoms will be available.

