7.1.3. Columbia Suicide Severity Rating Scale Criteria

Emergence of any positive (abnormal) response confirmed by the investigator on a clinician (or qualified designee) administered C-SSRS during the treatment phase of the study will be cause for discontinuation of study intervention.

Refer to the SoA (Section [1.3](#)) for data to be collected at the time of intervention discontinuation and follow-up and for any further evaluations that need to be completed.

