8.2.5. Suicidal Risk Monitoring and Management of Emergent Psychiatric Symptoms

GSK3640254 is not a central nervous system active drug nor is it being developed for a neurologic or psychiatric condition. However, given the risk of suicidal ideation identified with previous MI GSK3532795, all participants will undergo Screening using the C-SSRS administered by a clinician (or qualified designee); any positive (abnormal) response confirmed by the investigator, will exclude them from participating. A repeat assessment will be done during the treatment phase of the study. In case of positive (abnormal) response confirmed by the investigator, the participant will discontinue from the trial and the investigator will arrange for urgent specialist psychiatric evaluation and management.

As described in Section [7.1.4](#), new onset suicidal ideation at any time will result in immediate discontinuation from the trial and the investigator will arrange for urgent specialist psychiatric evaluation and management.

The definitions of behavioral suicidal events used in this scale are based on those used in the Columbia Suicide History Form [[Posner, 2007](#)]. Questions are asked on suicidal behavior, suicidal ideation, and intensity of ideation. Screening visit questions will be in

relation to lifetime experiences and current experiences (within the past 2 months) and all subsequent questioning in relation to the last assessment.

Emergent non-suicidal psychiatric AE evaluation and management:

- Any Grade 1 or 2 psychiatric AE: A Grade 1 or 2 psychiatric AE may result in additional unscheduled visits (in-clinic or at home) as clinically indicated. This may include a more in-depth assessment of AE through interview, additional unscheduled clinical labs, and/or imaging. Psychiatric consultation may be required at the discretion of the investigator. Any pharmacotherapy should be discussed with the medical monitor.
- Any Grade 3 or 4 psychiatric AE: As described in Section 7.1.4, a Grade 3 or 4 psychiatric AE will result in discontinuation from the trial and emergency psychiatric evaluation (including potential hospitalization and pharmacotherapy as indicated).

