Laboratory assessments (hematology, chemistry, urinalysis)	X		X				X		X	See Protocol Appendix 2 for specific tests to be performed. Day 2 samples in each period to be collected 24 hours after dosing.	
Pregnancy test	X								X	Serum testing at Day -1	

CONFIDENTIAL

209713

Procedure	Check-in	Periods 1, 2, and 3				Period 4 only				Notes	
		Day -1	Day 1	Washout			Day 1	Day 2	Days 3-4		Day 5 ¹
				Day 2	Days 3-5	Days 6-7					
Columbia-Suicide Severity Rating Scale	X				D7				X		
Genetic sample (optional)	X										
Study intervention: GSK3640254 200 mg (capsule or tablet)		X				X				Participants will fast overnight for at least 10 hours prior to dosing; be provided a moderate fat meal, a high fat meal, or no meal 30 minutes prior to dosing; and be provided standardized meals ≥4 hours postdose. See Protocol Section 4.1.	
Serial PK sampling		X	X	X		X	X	X	X	Blood collection for PK analysis of GSK3640254 will be collected within 40 minutes prior to dosing and 1, 1.5, 2, 2.5, 3, 3.5, 4, 4.5, 5, 6, 8, 12, 24, 48, 72, and 96 hours postdose in each period.	
AE review		←-----X-----→									
SAE review		←-----X-----→									
Concomitant medications		←-----X-----→									

AE = adverse event; D = day; ECG = electrocardiogram; PK = pharmacokinetic; SAE = serious adverse event.

1 Evaluations scheduled for Day 5 in Period 4 will also be performed for participants who discontinue early.

CONFIDENTIAL

209713

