10.9.5. Safety Tables

Safety: Tables					
No.	Population	IDSL / Example Shell	Title	Programming Notes	Deliverable [Priority]
Adverse Events (AEs)					
2.1.	Safety	AE1CP	Summary of Adverse Events by System Organ Class and Preferred Term		SAC
2.2.	Safety	AE1CP	Summary of Drug-Related Adverse Events by System Organ Class and Preferred Term		SAC
2.3.	Safety	AE16	Summary of Serious Adverse Events by System Organ Class and Preferred Term (Number of Subjects and Occurrences)		SAC
2.4.	Safety	AE1CP	Summary of Adverse Events of Special Interest by System Organ Class and Preferred Term		SAC
Laboratory: Chemistry					
2.5.	Safety	LB1	Summary of Clinical Chemistry Data		SAC
2.6.	Safety	LB1	Summary of Clinical Chemistry Changes from Baseline		SAC
Laboratory: Hematology					
2.7.	Safety	LB1	Summary of Hematology Data		SAC
2.8.	Safety	LB1	Summary of Hematology Changes from Baseline		SAC
Laboratory: Urinalysis					
2.9.	Safety	LB1	Summary of Urine Concentration		SAC
2.10.	Safety	LB1	Summary of Urine Concentration Changes from Baseline		SAC
ECG					
2.11.	Safety	EG2	Summary of ECG Values		SAC

CONFIDENTIAL

209713

Safety: Tables					
No.	Population	IDSL / Example Shell	Title	Programming Notes	Deliverable [Priority]
2.12.	Safety	EG2	Summary of ECG Changes from Baseline		SAC
Vital Signs					
2.13.	Safety	VS1	Summary of Vital Signs		SAC
2.14.	Safety	VS1	Summary of Vital Sign Changes from Baseline		SAC
C-SSRS					
2.15.	Safety	CSSRS4	Listing of C-SSRS Suicidal Ideation and Behavior Data	Only include participants who have suicidal ideation or behavior	SAC

CONFIDENTIAL

209713

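### Do the protocol and SAP set different C-SSRS schedules, and would the planned displays hide which one was followed?

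*Protocol*

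**What the plan says.** The protocol mentions the timing of the C-SSRS in several places.

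- Section 2.3.1 (risk table): "The C-SSRS will be administered during and after the treatment phase of the study".
- Section 2.3: "The C-SSRS assessment will also be administered by a clinician (or qualified designee) during the on-treatment portion of the study".
- Section 7.1.3: a confirmed positive response on a clinician- "administered C-SSRS during the treatment phase of the study will be cause for discontinuation of study intervention".
- Section 8.2.5: "A repeat assessment will be done during the treatment phase of the study".
- Section 1.3, Time and Events Table: the row labelled "Columbia-Suicide Severity Rating Scale" carries, in the text copy, a mark at check-in and one mark at the far right. Footnote 1 adds: "Evaluations scheduled for Day 5 in Period 4 will also be performed for participants who discontinue early".

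SAP Section 10.1.1 reproduces the schedule under a heading that calls it protocol-defined. Its row reads "Columbia-Suicide Severity Rating Scale X D7 X": check-in, Day 7 in the Days 6-7 washout column, and Period 4 Day 5.

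The only SAP display that names the C-SSRS is Table 2.15 (Section 10.9.5), with the programming note "Only include participants who have suicidal ideation or behavior".

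**The concern.** Two things look wrong.

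First, the two schedule rows differ, and the SAP's table of changes (Section 2.1) does not mention it. If the protocol row really has one post-dose mark, that single assessment cannot be both during and after treatment. The discontinuation criterion in Section 7.1.3 could then not act through a scheduled C-SSRS before any later dose. The protocol names neuropsychiatric safety as a major risk, so a gap between the stated mitigation and the schedule would matter.

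Second, a table restricted to participants with ideation or behavior is empty if everyone was assessed and negative, and equally empty if nobody was assessed. With the study stopped early, a reader of the report might not be able to tell the two apart.

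**Working it through.** **1. What the literal reading would imply.** With doses at the 7-day minimum spacing, dosing falls on study Days 1, 8, 15 and 22.

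- Period 4 Day 5 is 22 + 4 = study Day 26, which is 4 × 24 = 96 h after the last dose. Under the SAP's study-day rule (Section 10.4.1), Day -1 is the day before Day 1, so this is 26 days after check-in.
- Day 7 of Periods 1 to 3 is study Days 7, 14 and 21.

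| | Without Day 7 | With Day 7 |
|---|---|---|
| Later doses preceded by a scheduled post-baseline C-SSRS | 0 of 3 | 3 of 3 |
| Scheduled post-baseline C-SSRS, full design | 1 | 3 + 1 = 4 |
| Scheduled post-baseline C-SSRS, study as run | 1 | up to 2 + 1 = 3 |

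The last line assumes no Period 3 dose and that the early-discontinuation evaluations were done. The contrast is real only if Day 7 is truly missing from the protocol table.

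**2. Whether the protocol row can show that.** Count columns with the procedure name as 0. The visit columns are then check-in (1), Day 1 (2), Day 2 (3), Days 3-5 (4), Days 6-7 (5), and Period 4 Day 1, Day 2, Days 3-4 and Day 5 (6 to 9).

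| Row | Marks at |
|---|---|
| Protocol, pregnancy test | 1 and 9 |
| Protocol, serial PK sampling | 2, 3, 4, 6, 7, 8 and 9 |
| Protocol, C-SSRS | 1 and 10 |
| SAP, C-SSRS | 1, D7 at 5, and 9 |

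Column 10 is not a visit. The C-SSRS row has therefore been disturbed somewhere between its first and last marks, which is where a Day 7 entry would stand. The first page of the same table has also lost its Days 6-7 column heading. A row in this state cannot establish that an entry is absent.

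**3. Whether the SAP copy and the text agree.** The SAP row has no misplaced mark. With Day 7 in place, the washout assessments fall during the treatment phase (Sections 2.3, 7.1.3 and 8.2.5), and the assessment following the last dose can serve as the one after it (Section 2.3.1). Section 8.2.5 speaks of a repeat assessment without limiting it to one or ruling out a later one.

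**4. What the SAP's silence means.** Section 2.1 lists departures from the planned statistical analysis. A change to a visit schedule would not belong there, and silence is what one would see if nothing had changed.

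**5. What the displays cover.** There are 4 + 15 + 1 + 7 + 34 = 61 planned displays, and one names the C-SSRS. That count leaves out the other routes by which the same information reaches the report:

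- SAP Section 8.3 makes the suicide and self-injury query part of the adverse events of special interest, shown in Table 2.4 and Listing 19.
- All adverse events appear in Table 2.1 and Listing 14.
- Section 4.1 tracks deviations in participant assessment, and important ones go to Listing 4.
- A confirmed positive screening C-SSRS is exclusion criterion 20, and eligibility deviations go to Listing 5.

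**The case for a change.** The strongest reply is that loss of the Day 7 entry is not proven. Other entries of the same kind survived in the same protocol table, including a Day 7 note in the physical-examination row. That is correct: the text copy shows neither that Day 7 was in the source nor that it was not. But a claim that two documents conflict needs a legible row on each side, and one of these rows is damaged.

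It can also be said that the protocol's wording is uneven whatever the table shows: one section says during and after, another mentions only a repeat assessment during treatment. The SAP's on-treatment window of 5 days after the last dose would also take in Period 4 Day 5. The wording is loose but not contradictory, since one statement is less complete than the other. The window in SAP Section 10.2.1 is defined for laboratory, ECG and vital-sign data, not for the C-SSRS.

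Finally, Listing 4 covers important deviations only and gives no number assessed, so the named displays do not state C-SSRS completion directly. That stands as an observation. A count of participants assessed would be a courtesy to the reader. The SAP states in its introduction that only an abbreviated set of outputs will be produced after early termination, no objective or endpoint in protocol Section 3 names the C-SSRS, and no result changes with the count.

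**Conclusion.** No error in the plan is shown. The apparent schedule conflict rests on one protocol row whose last mark is a column out of place. The intact copy in SAP Section 10.1.1 is presented as the protocol's own schedule and is consistent with protocol Sections 2.3, 2.3.1, 7.1.3 and 8.2.5. The contrast of 0 against 3 later doses preceded by a scheduled C-SSRS is sound arithmetic but hypothetical.

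The positives-only Table 2.15 is a display preference that affects no estimate, endpoint or conclusion. Other safeguards do not depend on the scale's schedule: participants are housed throughout with continuous adverse-event evaluation, and Section 8.2.5 provides for discontinuation on new-onset suicidal ideation at any time.

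The conclusion assumes that a table row damaged in conversion is not evidence of what the source omits. If the source protocol table proved to lack Day 7, the schedule question would reopen, and the passages would have to be reconciled by the sponsor.

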2.3.2. Benefit Assessment

This is a study in healthy participants; no medical benefit will be derived by participants' participation.

2.3.3. Overall Benefit: Risk Conclusion

Given the preclinical profile of GSK3640254, the clinical profile of a structurally similar MI (GSK3532795), the clinical data gathered from Studies 207187 and 208131, and the planned clinical procedures and evaluations in this study, the potential risks to participants receiving GSK3640254 are low, evaluable, and manageable.

3. OBJECTIVES AND ENDPOINTS

Objectives	Endpoints

Primary
 
 To assess the relative bioavailability of GSK3640254 mesylate tablets and GSK3640254 mesylate capsules (in the presence of a moderate fat meal) To assess the effect of food (fasted, moderate fat meal, and high fat meal) on the PK of the GSK3640254 mesylate tablet formulation 	
 AUC(0-∞), AUC(0-t), Cmax, and Tmax for GSK3640254

Secondary
 
 To assess the safety and tolerability of GSK3640254 following single oral administration to healthy participants under fasted or fed (moderate fat or high fat) conditions To characterize the PK of GSK3640254 	
 Safety and tolerability parameters for AEs/SAEs, observed and change from Baseline clinical laboratory assessments, ECGs, and vital sign measurements tlag, t1/2, CL/F, and Vz/F for GSK3640254 GSK3640254 PK concentrations in plasma

AE = adverse event; AUC(0-∞) = area under the plasma concentration-time curve from time zero extrapolated to infinity; AUC(0-t) = area under the plasma concentration-time curve from time zero to time t; CL/F = apparent oral clearance; Cmax = maximum observed concentration; ECG = electrocardiogram; PK = pharmacokinetics; SAE = serious adverse event; t1/2 = apparent terminal phase half-life; tlag = lag time for absorption; Tmax = time of maximum observed concentration; Vz/F = apparent volume of distribution.

4. STUDY DESIGN

4.1. Overall Design

This is a Phase 1, randomized, open-label, single-dose, 4-period crossover study to compare the relative BA of a tablet formulation of GSK3640254 with the capsule

formulation and to assess the effect of food on the PK of the tablet formulation in healthy participants.

The study will consist of a Screening period and 4 sequential treatment periods with a single dose of study intervention per treatment period. Prior to dosing on Day 1 of Period 1, participants will be randomly assigned to 1 of 4 treatment sequences (ABCD, BADC, CDAB, or DCBA). Participants will receive each of the following treatments administered as 1 treatment per period:

- Treatment A: GSK3640254 200 mg (single dose given as 2 × 100-mg capsules) administered under moderate fat conditions (reference).
- Treatment B: GSK3640254 200 mg (single dose given as 2 × 100-mg tablets) administered under moderate fat conditions (test).
- Treatment C: GSK3640254 200 mg (single dose given as 2 × 100-mg tablets) administered under fasted conditions (reference).
- Treatment D: GSK3640254 200 mg (single dose given as 2 × 100-mg tablets) administered under high fat conditions (test).

To ensure adequate washout, there will be at least 7 days between each dose of study intervention, with an allowance window of 4 hours (i.e., 7 days minus 4 hours) to allow flexibility in scheduling participants for dosing at the clinic. Treatments A, B, and D will be administered in the fed state. Participants will fast overnight for at least 10 hours prior to dosing and will receive a moderate fat (Treatments A and B) or high fat (Treatment D) meal 30 minutes prior to dosing. Dose administration will occur within 5 minutes of completion of meal consumption. Participants will not receive any further food until 4 hours after dosing. Treatment C will be administered in the fasted state. Participants will fast overnight for at least 10 hours prior to dosing and until 4 hours after dosing.

Pharmacokinetic blood samples for the analysis of GSK3640254 will be collected prior to dosing (0 hour) on Day 1 and up to 96 hours postdose in Periods 1, 2, 3, and 4.

Safety and tolerability will be assessed by monitoring and recording of AEs, clinical laboratory test results, vital sign measurements, 12-lead ECG results, and physical examination findings.

Study assessments will be performed as indicated in the SoA (Section 1.3). Study participants will be confined to the clinic from Day –1 until discharge on Day 5 of Period 4. The total duration of the study, including Screening, is approximately 54 days.

